Methadone in Pediatric Anesthesia II

PI: [name] MD, MBA
Associate Professor,
Director of Quality Improvement,
Department of Anesthesiology, BO 8054
[contact]
[contact]

Co-PI: [name] PhD
Russell D. and Mary B. Shelden Professor of Anesthesiology
Director, Division of Clinical and Translational Research
Department of Anesthesiology, Box 8054
T [contact]
F [contact]
[contact]

Co-Investigators: [name] MD
Associate Professor of Anesthesiology
Box 8054,
[contact]

Original: 02/02/2013
Amendment 1: 12/5/13
Amendment 2: 4/16/14
Amendment 3: 09/10/2014

Amendment 1, 12/5/2013: Administration of PROMIS questionnaire to be administered by the research team to the patient on a tablet device.

Rationale: To help determine patient's preoperative expectations and functional status as impacted by their medical condition requiring this surgical procedure.

CONFIDENTIAL

Amendment 2, 4/16/2014: Administration of a questionnaire to the participant's parent or legal guardian

Rationale: To help determine from the primary caregiver the influence of the environment, social and psychological, on post-operative pain.

CONFIDENTIAL

Amendment 3, 09/10/2014: Change in dosage range for intraoperative administration of methadone from 0.4-0.5mg/kg Ideal Body Weight to 0.3 – 0.5mg/kg Ideal Body Weight (IBW)

Rationale: Postoperative management of pain for the pediatric spinal surgery population has changed over the course of time since the completion of our last research project (HRPO# 201107357). The previous study had demonstrated that 0.3mg/kg methadone was not effective in reducing postoperative opioid consumption. Currently, patients are prescribed additional drugs such as gabapentin and methocarbamol, with potential for interaction with all opioids. Based on our observations with this current protocol to date, we anticipate that escalation of methadone dosages beyond 0.4mg/kg (ideal body weight) may not be required. We feel that routine postoperative use of gabapentin and methocarbamol require re-evaluation of intraoperative methadone dosing at 0.3mg/kg (IBW) for this population under current standard of care pain management.

CONFIDENTIAL

Abstract

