The μ -opioid receptor agonist methadone is frequently used in adult anesthesia and adult pain therapy. Methadone has an extremely long half-life, which confers therapeutic advantage by providing more stable plasma concentrations and long-lasting pain relief. Methadone perioperative pharmacokinetics in adults is well characterized. Methadone is also frequently used in children. Previous work by our group demonstrated that pharmacokinetics of methadone in adolescents are very similar to that in adults, but that doses used for major spinal surgery (0.1-0.3 mg/kg) were insufficient to have a significant opioid-sparing effect. This current investigation aims to study opioid sparing effects of higher doses of methadone (0.3 - 0.5 mg/kg) in adolescents undergoing posterior spinal fusion. Additionally, we will determine the pharmacokinetics of the higher doses of IV methadone administered intra-operatively.

CONFIDENTIAL

SYNOPSIS

Study Title	Methadone in Pediatric Anesthesia II
Objective	Multiple arm, randomized controlled trial to evaluate the efficacy of a single dose of intraoperative methadone in reducing post-operative pain and opioid consumption in adolescents undergoing posterior spinal fusion. Our secondary goal is to determine the pharmacokinetics of IV methadone in children (0.3 - 0.5 mg/kg).
Study Period	Planned enrollment duration: Approximately 2 years. Planned study duration: Approximately 6 days per subject
Number of Patients	60 evaluable subjects
Study Medication Administration	60 evaluable patients will be randomized 2:1 to receive intraoperative IV methadone HCL, 0.3 – 0.5mg/kg, or serve as controls and will not receive any methadone. Control subjects will receive standard of care treatment per the attending anesthesiologist.

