Study Design	Randomized, controlled, modified, Dixon up and down dose-finding design (1). Patients receive standard monitoring for anesthesia and postoperative care. Surgical and anesthesia (except for opioid use) care are not altered for study purposes. All patients are induced by propofol and muscle relaxants. In the first cohort, subjects are randomized 1:2 to either control (standard intraop opioid at anesthesiologists' discretion) or methadone HCl (0.4 mg/kg ideal body weight, IBW). Based on an interim analysis for the initial treatment dose (0.4mg/kg), the second cohort will be randomized 1:2 to either control (standard intraop opioid) or methadone HCl (0.3 mg/kg ideal body weight, IBW). Subjects in the study groups will receive methadone (IV bolus, after induction of anesthesia) as their primary intraoperative opioid, rather than leaving the choice of intraoperative opioid to the anesthesiologist. Intraoperative breakthrough pain will be treated at the discretion of the anesthesiologist with fentanyl. In the control groups, intraoperative opioid administration will be left at the discretion of the anesthesia providers. Patient controlled analgesia as prescribed by the clinical team, using hydromorphone or morphine, will be used to treat postoperative pain relief.
Inclusion and Exclusion Criteria	Inclusion Criteria 1. Age 11-18 years 2. Undergoing general anesthesia and idiopathic posterior spinal fusion surgery with anticipated postop inpatient stay of > 3 days 3. Signed, written, informed consent from legal guardians and assent from patient Exclusion Criteria 1. History of liver or kidney disease. 2. Females who are pregnant or nursing. 3. Developmental delay and/or neuromuscular scoliosis
Measurements	Total intraoperative and postoperative care unit (PACU) opioid administration will be recorded from the patient's medical record. Daily opioid consumption will be calculated from the PCA utilization and electronic medical records (EMRs) for up to 6 postoperative days. Pain intensity will be assessed using the Wong-Baker FACES scale. Pain relief is also assessed using a Colored-Visual Analog Scale. Blood and urine samples will be collected for 96 hrs after methadone dosing for determination of methadone and metabolite concentrations by HPLC-mass spectrometry. Subjects will be genotyped for major polymorphisms of the methadone metabolizing enzyme CYP2B6.

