Methadone is a μ opioid agonist which is highly efficacious in the treatment of acute, chronic, neuropathic, and cancer pain(5). In adults it is increasingly being used as a first-line analgesic. Methadone is highly efficacious in adult anesthesia and postoperative pain(6,7). The typical dose for adult anesthesia is 20 mg (nominally 0.3 mg/kg) at the beginning of anesthesia. Methadone is advantageous because it has slow elimination, resulting in prolonged effect and significantly diminished need for postoperative analgesics. Reducing postop opioid analgesic use also decreases the potential for opioid-related side effects. Methadone has a long half-life, averaging 24-36 hours in healthy adults and adolescent patients (12). It has no active metabolites or pro-drug forms. Methadone is metabolized in the liver by cytochrome P450 CYP2B6 (8-10). Methadone is also widely used in children, particularly in pain treatment(11). In infants and children younger than 10 yrs (mean age 4 yrs), the initial daily dose of methadone did not exceed 0.2–0.4 mg/kg/day, and daily methadone doses rarely exceeded 0.6 mg/kg.

Perioperative analgesia remains a major challenge for physicians who care for patients undergoing complex spine surgery. Many patients are controlled by opioid analgesic that can result in postoperative adverse events. We propose to compare the two different doses of methadone in reducing

the postoperative opioid consumption and reduction in pain scores.

A recent study by our group demonstrated that the pharmacokinetics of methadone enantiomer disposition in adolescents were similar to that of healthy adults (12). Another study by Stemland et al used a three compartmental model to analyze time-concentrations profile of single dose of 0.25mg/kg of methadone. They concluded that the pharmacokinetic profile in adolescents was similar to that of adults. They also observed a rapid redistribution after single bolus of methadone, hence producing inadequate plasma concentrations of the drug for postoperative analgesia. This suggests that in order to improve efficacy of methadone, higher dose than 0.3 mg/kg of methadone or continuous infusion of methadone may be needed (13).

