6.1. Preoperative and Intraoperative Period

Parents and patients will be asked to complete a questionnaire prior to the child's surgery. This will take approximately 5 minutes. Participants can choose to complete the survey and not participate in the randomized part of the study. The questionnaire is to determine if factors such as anxiety and social economic attributes interact with each other prior to surgery. If only participating in the questionnaire information regarding demographic data, pain scores and pain treatment will be collected from the patients' medical record.

Patients will receive standard physiologic monitoring for anesthesia and postoperative care. Using a modified Dixon up and down dose finding method, subjects in the first cohort are randomized 1:2 to receive either control (standard intraop opioid) or methadone HCl (0.4 mg/kg ideal body weight, IBW). In the second cohort, subjects are randomized 1:2 to receive either control (standard intraop opioid) or methadone HCl (0.3 mg/kg ideal body weight, IBW).

Anesthesia and surgical care will not be altered for the purposes of this investigation, except that subjects in groups I and II, will receive methadone as their intraoperative opioid, rather than leaving the choice of intraoperative opioid to the anesthesiologist (patients typically may get methadone or any other opioid). The control group patients will receive intraoperative analgesia with opioids other than methadone left at the discretion of their anesthesiologist. Additional

randomized cohorts may be included to study IV methadone HCl doses within the range of 0.3 – 0.5mg/kg IBW, based on interim study findings and analysis.

6.2. *Administration of Study Medication.*

Methadone is administered as an IV bolus after induction of anesthesia and after an arterial line is placed. Methadone hydrochloride is available commercially as a solution for injection of 10 mg/ml. Based on our experience, we believe that additional postoperative opioids will still be needed, but that increasing methadone doses will result in lessened postoperative opioid use.

6.3. *Assessments.*

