9.2.4. Maximum plasma EDDP concentration

9.2.5. AUC (plasma EDDP)/AUC (plasma methadone)

9.2.6. Cmax (plasma EDDP)/Cmax (plasma methadone)

9.2.7. Urine concentration of methadone and EDDP

9.2.8. Side effects of opioids

9.3. Analysis.

9.3.1. Sample Size- we decided to use our pilot study data which looked into the pharmacokinetics of methadone in pediatric surgical patients attending St. Louis Children Hospital. This is actually the pooling place for the present study and therefore the information provided is a "true" sample of the data to be collected. The pilot study revealed that patients undergoing spinal fusion surgery used an average of 274 mg of morphine equivalents within 72 hours post-surgery with a standard deviation of 82 mg. Based on this information and assuming a 2-sided test of two independent sample means with α 0.05, we were able to estimate that the proposed study will have at least 80% power to detect 30% decrease in the total postoperative consumption of morphine or morphine equivalents among the patients assigned to the two treatment groups combined when compared to the control group

patients. Specifically, with a total sample of approx. 60 patients assigned equally across study groups (1:2 randomization), we will have adequate statistical power to detect a clinically meaningful reduction of opioid use in patients receiving a single dose of methadone before incision.

To study the effect size between two groups, power calculations were made with alternative mean differences in morphine consumption over 72 hours post-surgery with assumed variation range and a 2-sided test with $\alpha = 0.05$. Based on our conservative assumptions, we found that, with a sample as small as 20 in each group, we will have 80% power to detect a minimum difference between 10 and 20 mg of morphine use, depending on the observed variability between the two groups.

9.3.2. Statistical Analysis- Baseline characteristics of the cohort will be described. Demographics data including race, sex, and age at study entry will be analyzed using chi-square and t- test appropriate. Total daily opioid consumption and pain scores using both Wong-Baker FACES and colored visual analogue scale, will be compared between the groups. Outcome measures will be expressed by the mean and standard deviation. Group outcomes will be compared across the two or three groups, using t-test and/or analysis of variance, ANOVA and MANCOVA to account for potential cofounders.

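### Does sizing the trial on both methadone doses combined leave it underpowered if 0.3 mg/kg does little?

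*Combined protocol and SAP*

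**What the plan says.** Section 9.3.1 (Sample Size) takes a pilot mean of 274 mg morphine equivalents over 72 hours with SD 82 mg. It claims at least 80% power, two-sided 0.05, for a "30% decrease in the total postoperative consumption of morphine or morphine equivalents among the patients assigned to the two treatment groups combined", compared with control. The Synopsis sets the total: "60 evaluable patients will be randomized 2:1 to receive intraoperative IV methadone HCL, 0.3 – 0.5mg/kg", or control.

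The doses come in steps. The first cohort is at 0.4 mg/kg. For the second the Synopsis says "Based on an interim analysis for the initial treatment dose (0.4mg/kg), the second cohort will be randomized 1:2 to either control" or 0.3 mg/kg. Section 6.1 adds that further randomized "cohorts may be included to study IV methadone HCl doses within the range of 0.3 – 0.5mg/kg IBW, based on interim study findings".

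Several statements point to a weaker effect at 0.3 mg/kg. The Abstract says that "doses used for major spinal surgery (0.1-0.3 mg/kg) were insufficient to have a significant opioid-sparing effect". Amendment 3 says "The previous study had demonstrated that 0.3mg/kg methadone was not effective in reducing postoperative opioid consumption". Section 2 says a "higher dose than 0.3 mg/kg of methadone or continuous infusion of methadone may be needed". Section 6.2 expects that "increasing methadone doses will result in lessened postoperative opioid use". Amendment 3 also explains why 0.3 mg/kg is looked at again: gabapentin and methocarbamol have since become routine.

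Section 9.3.2, the analysis section, does not prescribe combining the doses. It compares two or three groups by t-test and/or analysis of variance, with MANCOVA for confounders.

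**The concern.** A combined 30% drop is an average over two doses. The plan gives no expected reduction for either dose, and its own background suggests that they differ. If 0.3 mg/kg did nothing, 0.4 mg/kg would have to cut use by 60% for the average to be 30%.

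Two things would be at stake. A true 30% reduction at 0.4 mg/kg could be missed because it is averaged with a dose that does less. And a significant combined result would credit methadone in general without showing which dose worked, in a trial described as dose-finding. Section 9.3.2 does not say which comparison decides, so the reader cannot be sure that the weaker test is not the one that counts.

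**Working it through.** **Inputs from section 9.3.1:** control mean 274 mg, SD 82 mg, two-sided 0.05, about 60 patients at 1:2. Equal assignment across study groups is read as 20 at 0.4 mg/kg, 20 at 0.3 mg/kg and 20 controls. **Assumption:** the reduction at each dose is not in the documents, so 0.4 mg/kg is set at 30% and 0.3 mg/kg is varied.

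**1. The plan's figure.** Difference = 0.30 × 274 = 82.2 mg. Standard error at 40 v 20 = 82 × √(1/20 + 1/40) = 22.46 mg. Ratio = 82.2 / 22.46 = 3.66. Power = Φ(3.66 − 1.96) = Φ(1.70) = 95.5%, or 94.9% by the noncentral t. The claim of at least 80% holds with room to spare. The smallest difference with 80% power is (1.96 + 0.84) × 22.46 = 62.9 mg, or 23% of 274 (64.0 mg by the t-test).

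**2. Unequal doses, combined test.** The average reduction is (30% + r) / 2, where r is the reduction at 0.3 mg/kg. Mixing two doses also widens the methadone arm. At r = 0 its SD is √(82² + 41.1²) = 91.7 mg. The simulated t-test includes this spread; the noncentral t with SD 82 does not.

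| r at 0.3 mg/kg | Average | Difference (mg) | Power, SD 82 | Power, simulated |
|---|---|---|---|---|
| 30% | 30% | 82.2 | 95% | 95% |
| 20% | 25% | 68.5 | 85% | 85% |
| 15% | 22.5% | 61.7 | 77% | 76% |
| 10% | 20% | 54.8 | 67% | 64% |
| 0% | 15% | 41.1 | 44% | 37% |

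At r = 0 the variants run from 37% (equal-variance t-test) through 40% (Welch) to 45% (normal approximation with SD 82: 41.1 / 22.46 = 1.83; Φ(1.83 − 1.96) = 44.8%). Simulated power is 79.6% at r = 17% and 80.6% at 17.5%.

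**3. The three-group comparison in section 9.3.2.** At 20/20/20 with 0.4 mg/kg at 30%, the F test has 90% power at r = 0, 81% at 10%, 80% at 15% and 90% at 30%. It does not by itself identify the dose.

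**4. The alternative: 0.4 mg/kg alone v all 20 controls.** Standard error = 82 × √(1/20 + 1/20) = 25.93 mg. Ratio = 82.2 / 25.93 = 3.17. Power = 88.7% (normal) or 87.1% (t), whatever 0.3 mg/kg does. The combined test matches this at r of about 22% and beats it above that. If both doses give 30%, the combined test has 95%.

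**5. Drift between cohorts.** All 0.4 mg/kg patients are in cohort 1, but half of the merged controls are in cohort 2. A 40 mg shift in use therefore biases the single-dose comparison by 40 / 2 = 20 mg. Its simulated false positive rate rises to 11%, while the combined test, with both arms split equally over the cohorts, stays at 4.4%. If use falls by 40 mg, power for a true 30% reduction at 0.4 mg/kg drops from 87% to 64%. The drift-proof version uses only the cohort's own controls, 20 v 10: standard error = 82 × √(1/20 + 1/10) = 31.76 mg, ratio 2.59, power 73.5% (normal) or 70.5% (t).

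**The case for a change.** The strongest case for a change does not rest on a zero effect. Combined power is below the stated 80% whenever 0.3 mg/kg gives less than about 17%, and the plan's own background makes a weak effect there plausible. Ordered tests, highest dose first, would hold the error at 5% in the absence of drift, need no extra patients and show which dose worked. The price would be 87% instead of 95% at the first step if both doses give 30%, with 79% for both being significant. The 70% from own controls is also still well above 37% to 45%.

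The arithmetic stands. So does the remark that section 9.3.2 names no deciding contrast: at zero effect for 0.3 mg/kg, the combined test and the F test differ by some 50 percentage points in power, so the choice is best made before the data are seen. The same goes for the endpoint, since 9.1.1 counts opioids over the hospitalization and 9.3.1 over 72 hours.

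It does not stand that the plan's efficacy test averages all doses; only the sizing does. Nor does the previous study's lack of effect fix the reduction at zero under changed co-medication. And the ordered scheme swaps one weakness for another, because dose is tied to cohort. The F test shares that exposure when controls are merged. If a third dose entered within the 60, a first step of about 13 v 20 would have some 78% power, and its failure would block the test of 0.4 mg/kg.

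**Conclusion.** No change follows. The power statement is correct for the effect it names, 95% against a claim of at least 80%. The fall to 37–45% needs three assumptions together: a 20/20 dose split, 30% at 0.4 mg/kg and exactly nothing at 0.3 mg/kg. With 15% to 20% at 0.3 mg/kg, combined power is 76% to 85%.

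Combining the doses also suits Aim 1.1, which asks about a single dose of methadone and not about ranking doses. Randomization at 1:2 within each cohort keeps that contrast balanced over time. Which contrast is better depends on two unknowns: whether the reduction at 0.3 mg/kg exceeds about 22%, and how stable opioid use is between cohorts. Reasonable statisticians could choose either. What is left open (the deciding contrast, whether controls are merged, the time window, what the interim analysis tests) is detail that analysts can settle sensibly in writing before the data are seen. None of it corrects a stated figure.

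### The claim that 20 per group gives 80% power for a 10–20 mg difference does not follow from the reported SD of 82 mg, which gives about 75 mg

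*Combined protocol and SAP*

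**What the plan says.** Section 9.3.1 contains two power statements.

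The first rests on pilot data. Spinal fusion patients "used an average of 274 mg of morphine equivalents within 72 hours post-surgery with a standard deviation of 82 mg", and the section presents that pilot as representative of the data to be collected. From it the plan derives at least 80% power for a 30% decrease "among the patients assigned to the two treatment groups combined when compared to the control group", with about 60 patients randomized 1:2.

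The second concerns a comparison of two groups that are not named. Here "power calculations were made with alternative mean differences in morphine consumption over 72 hours post-surgery with assumed variation range", again two-sided at 0.05. On assumptions it describes as conservative, and for groups of only 20 patients, the plan concludes: "we will have 80% power to detect a minimum difference between 10 and 20 mg of morphine use". It makes the exact figure conditional on how variable the data turn out to be. The variation range is given neither here nor elsewhere in the documents.

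Section 2 (Background) announces a comparison of doses: "We propose to compare the two different doses of methadone in reducing". The outcomes it names for this are opioid use after surgery and pain scores.

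**The concern.** Both statements concern the same outcome over the same 72 hours, yet their precision differs greatly. The first uses an SD of 82 mg to detect a difference of 82.2 mg (30% of 274 mg). The second claims to resolve 10 to 20 mg, which is 4% to 7% of the same mean, with fewer patients. Only a far smaller SD could produce that, and none is reported.

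This is the plan's only power statement for a comparison of two groups of 20. A reader would conclude that such a comparison can resolve small differences. If two methadone doses were compared and the result was not significant, the stated sensitivity would invite the reading that the doses work equally well, when the comparison could reliably detect only a large difference.

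**Working it through.** **Inputs, all from section 9.3.1.** Pilot mean 274 mg and SD 82 mg (72 hours); two-sided α = 0.05; power 80%; 20 per group for the disputed statement; about 60 patients at 1:2, read as 20 control and 40 methadone, for the main one.

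**Method.** Two-sample t-test with noncentral t power. Standard error SE = SD × √(1/n₁ + 1/n₂); noncentrality = difference / SE; degrees of freedom n₁ + n₂ − 2.

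**1. Main calculation.**
- 30% of 274 = 82.2 mg.
- SE = 82 × √(1/20 + 1/40) = 22.46 mg; noncentrality = 82.2 / 22.46 = 3.66.
- Power = 94.9%, so the claim of at least 80% holds.

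**2. Disputed calculation at the reported SD.**
- SE = 82 × √(2/20) = 25.93 mg.
- 10 mg: noncentrality 0.386; power 5.66% (upper tail) + 0.97% (lower tail) = 6.6%.
- 20 mg: noncentrality 0.771; power 11.35% + 0.33% = 11.7%.
- Difference detectable with 80% power: 74.5 mg. The normal approximation gives (1.960 + 0.842) × 25.93 = about 72.6 mg.
- 74.5 / 20 = 3.7 and 74.5 / 10 = 7.5, so the true figure is 3.7 to 7.5 times the stated one. 74.5 / 274 = 27%.
- Patients per group needed at SD 82 mg: 1057 for 10 mg and 265 for 20 mg.

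A simulation of 200,000 trials per setting gave 0.066 and 0.115, and 0.801 at 74.5 mg.

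**3. The SD that the stated figure requires.** The detectable difference is proportional to the SD: 74.5 / 82 = 0.909 mg per mg of SD.
- 10 mg: 10 / 0.909 = 11.0 mg, which is 13% of 82.
- 20 mg: 20 / 0.909 = 22.0 mg, which is 27% of 82.

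**4. Other readings.**

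| Reading | Result |
|---|---|
| One-sided test, 20 vs 20 | detects 65.7 mg |
| 20 vs 40 | detects 64.0 mg |
| 30 vs 30 | detects 60.3 mg |
| Per-day SD, 82/√3 = 47.3 mg | detects 43.0 mg |
| Per-day SD, 82/3 = 27.3 mg | detects 24.8 mg |
| 10% and 20% of 274 mg, 20 vs 20 | power 18% and 54% |
| Covariate adjustment | needs a correlation of about 0.96 to 0.99 |

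None gives 80% power for 10 to 20 mg under credible conditions.

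**5. Could the pilot SD simply be imprecise?** The pilot size is not given, so I assume values. With normal data, the lower 95% limit for a true SD estimated at 82 mg is 49 mg for n = 5, 56 mg for n = 10 and 62 mg for n = 20. None comes near 22 mg.

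**6. Sensitivity to the SD (20 vs 20; 60 and 41 mg are illustrative assumptions).**

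| SD | Detectable difference, 80% power | As % of 274 mg |
|---|---|---|
| 82 mg | 74.5 mg | 27% |
| 60 mg | 54.5 mg | 20% |
| 41 mg (half the pilot SD) | 37.3 mg | 14% |

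Even at 41 mg, power is 11.7% for 10 mg and 32.4% for 20 mg.

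**The case against.** The plan does not say that 10 to 20 mg is detectable at an SD of 82 mg. It appeals to a separate assumed range and makes the result conditional on the observed variability, so strictly no slip in arithmetic can be shown, only an undisclosed input. That is fair as a description, but it does not rescue the sentence. The missing range is not supplied, and an SD of 11 to 22 mg is optimistic beside the pilot, not conservative. The rationale for Amendment 3 says "Postoperative management of pain for the pediatric spinal surgery population has changed over the course of time", which could alter the SD, but it reports no smaller one.

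The consequence is also limited. The sample size of 60 rests on the first statement, which holds. The groups are unnamed. If one dose against 20 controls is meant, power for the 30% effect is still 87.1%. Reading the sentence as dose versus dose is an inference from section 2, assumes that the 40 methadone patients split 20/20, and must allow for section 6.1, which permits further cohorts. The plan contains no equivalence claim or rule based on non-significance between doses. These points stand and limit the severity, but not the error.

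Two further points are accepted:
- **Base of the percentages.** They refer to the pilot mean. If methadone achieved the targeted decrease, the methadone mean would be 274 − 82.2 = 191.8 mg, and 74.5 mg would be about 39% of it.
- **Sequential cohorts.** The doses are studied one after the other, each randomized against its own controls (section 6.1). A dose-versus-dose contrast is therefore not a concurrent randomized comparison, which a simple confidence interval would not reflect.

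**Conclusion.** The concern holds. As written, the sentence states a sensitivity that the design does not deliver at the only SD the documents report: about 75 mg is detectable with 20 per group, not 10 to 20 mg. This rests on a two-sample t-test, equal SDs of 82 mg in both groups and a 20/20 split. The conclusion survives a halving of the SD. The main power statement and the planned 60 patients stand. The point should be fixed, but it does not undermine the trial's primary comparison.

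**What to change.** In section 9.3.1, state the SD range used and justify it against the pilot SD of 82 mg. If that cannot be done, replace the sentence with, for example: *With 20 patients per group and the pilot SD of 82 mg, a two-sided 5% test has 80% power to detect a difference of about 75 mg in 72-hour morphine equivalents (27% of the pilot mean of 274 mg).* Name the two groups. Because Amendment 3 reports changed pain management, add the detectable difference for a short range of SDs, labelled as assumptions (41, 60 and 82 mg give 37, 55 and 75 mg).

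Optional: report pairwise differences with 95% confidence intervals. The expected half-width at SD 82 mg is 2.024 × 25.93 = about 52 mg. State that a non-significant difference between doses will not be read as equal effect, and that a dose-versus-dose contrast runs across sequential cohorts.

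The cost is rewording one paragraph and accepting a less favourable stated sensitivity. No extra patients are needed.

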6.3.1. Pain Assessment – Acute postoperative pain will be managed by St. Louis Children's Hospital pain services. Assessments are made in the postoperative period by a trained member of the research team blinded to intraoperative use of methadone. These will be conducted on each post-operative day until discharge or post op day 6, whichever comes first. Pain intensity is assessed using the Wong-Baker FACES scale employed by the inpatient nursing staff and previously validated (9). Pain relief is also assessed using a Colored-Visual Analog Scale. Other questions regarding pain relief and comfort may be given using a tablet. Sedation is assessed using a five-point scale (patient fully alert – not arousable). Itching and nausea are assessed using a five-point verbal scale (none, mild, moderate, severe or excruciating).

6.3.2. Pharmacokinetics – Pharmacokinetics studies will be performed for all patients in methadone treatment groups. Blood samples (approx 3 ml each) will be obtained before methadone and at approx 0.08, 0.5, 1, 1.5, 2, 3, 4, 6, 8, 10, 12, 24, 48, 72, and 96 hr after IV methadone administration. Blood samples will be drawn from the arterial line for the first 24 hours and then from the venous lines or collected with routine labs. Total amount of blood drawn will be approx. 48 mls for pharmacokinetic testing for up to four days. Blood will only be collected while the patient is hospitalized; if the patient is discharged from the hospital no further collections will be made.

6.3.3. CYP Genotyping – For all patients, 5 ml of blood will be drawn for CYP2B6 genotyping. Genotyping will be performed at the WUSTL Genome Technology Access Center (GTAC).

6.3.4. Urine samples- For all patients, 24 hour- urine collections will be conducted for up to 96 hours after surgery.

6.4. *Postoperative Period*

Patients receive standard of care analgesia using patient control analgesia method, primarily with hydromorphone or morphine as determined by the treating physician. Postoperative

care is not altered for purposes of this study.

7. Data Collection and Monitoring.

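### Section 9.3.2 tests daily opioid use and pain scores without fixing a day or summary, controlling error across days, or handling days after discharge

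*Combined protocol and SAP*

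**What the plan says.** Section 7.2 totals opioid use, in morphine equivalents, for each 24-hour period. Sections 6.3.1 and 7.1 schedule daily pain assessments, and 6.3.1 sets their limit: "These will be conducted on each post-operative day until discharge or post op day 6, whichever comes first". Eligibility (4.1.2) asks only for an expected stay of more than 3 days, so the number of days per patient will vary.

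On analysis, 9.3.2 states: "Total daily opioid consumption and pain scores using both Wong-Baker FACES and colored visual analogue scale, will be compared between the groups". It adds that outcomes will be compared across two or three groups "using t-test and/or analysis of variance, ANOVA and MANCOVA", with adjustment for confounders. It says nothing about a chosen day, a per-patient summary, a within-patient model, an adjustment for several days, or days after discharge.

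These outcomes rank high. The Synopsis counts daily cumulative opioid use among the primary outcomes, and 9.1.2 lists pain and pain relief scores as primary with no time point. The other primary assessment, in 9.1.1, is one opioid total per patient over the hospital stay. The power statement in 9.3.1 also rests on one total per patient, over 72 hours.

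**The concern.** Each patient contributes up to six correlated daily values on each of three outcomes: opioid use, FACES score and coloured-scale score. The methods named can be applied to such data in several ways, and 9.3.2 does not choose among them:

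- one test per day, each at 5%;
- one test on all patient-days together;
- one multivariate test on the vector of days;
- one test on a per-patient summary.

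These differ in error rate, in what they estimate, and in which patients they keep. If the choice is left until the data are seen, a significant result on one favourable day could be reported as a primary finding, and the reader could not tell how many days were examined. Early discharge adds a second risk. Length of stay may depend on recovery, so an analysis that needs every day could retain mainly the slower-recovering patients.

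**Working it through.** **1. The plan's own figure.** Inputs from 9.3.1: patients "used an average of 274 mg of morphine equivalents within 72 hours post-surgery with a standard deviation of 82 mg"; a 30% decrease; two-sided α 0.05. From the Synopsis: 60 evaluable patients, one third of them controls, taken as 20 v 40.

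- Difference: 0.30 × 274 = 82.2 mg.
- Standard error: 82 × √(1/20 + 1/40) = 22.46 mg.
- Ratio: 82.2 / 22.46 = 3.66.
- Power: Φ(3.66 − 1.96) = Φ(1.70) ≈ 95.5% (94.9% with the noncentral t).

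The plan claims "at least 80% power to detect 30% decrease in the total postoperative consumption of morphine or morphine equivalents", so its statement holds as a lower bound. It concerns one value per patient, and the daily-data question does not touch it.

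**2. Set-up for the daily data.** The documents give no within-patient correlation ρ, so 0.3 to 0.7 is an assumption. Simulation under no treatment effect: 20,000 trials, 20 v 40 patients, normal data, equal correlation between days, no missing days, K = 3 or 6 days.

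| Days K | ρ | Single-day test | At least one day p < 0.05 | Patient-days pooled | Multivariate test on days | Per-patient mean |
|---|---|---|---|---|---|---|
| 3 | 0.3 | 5.0% | 13.7% | 12.3% | 5.1% | 4.9% |
| 3 | 0.5 | 5.0% | 12.8% | 16.8% | 4.8% | 4.8% |
| 3 | 0.7 | 4.9% | 10.9% | 20.4% | 5.0% | 4.8% |
| 6 | 0.3 | 5.1% | 24.6% | 22.0% | 5.0% | 5.3% |
| 6 | 0.5 | 4.9% | 20.7% | 29.2% | 5.0% | 4.8% |
| 6 | 0.7 | 5.0% | 16.8% | 36.7% | 5.0% | 5.0% |

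The simulation standard error is at most √(0.37 × 0.63 / 20,000) ≈ 0.3 percentage points. A repeat with 100,000 trials per setting agreed within one point on the single-day, any-day, pooled and per-patient-mean columns.

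**3. Check on the any-day column.** With independent days, the chance of at least one false positive is 1 − 0.95^K: 14.3% for K = 3 and 26.5% for K = 6. Correlation lowers it, as the table shows. This inflation comes from multiplicity, not from ignored correlation.

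**4. Check on the pooled column.** Pooling understates the variance of a group mean by the factor 1 + (K − 1)ρ. The false-positive rate is therefore about 2 × [1 − Φ(1.96 / √(1 + (K − 1)ρ))].

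- K = 3, ρ = 0.3: √1.6 = 1.265; 1.96 / 1.265 = 1.55; rate ≈ 12%.
- K = 6, ρ = 0.7: √4.5 = 2.121; 1.96 / 2.121 = 0.924; rate ≈ 36%.

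Both agree with the simulation. This inflation does come from ignored correlation, and it rises with ρ.

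**5. Missing days.** The multivariate column assumes complete vectors. Under 6.3.1 assessment ends at discharge, so incomplete vectors are part of the design. Standard MANCOVA software excludes such patients.

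**The case against.** A reader might infer that the methods in 9.3.2 give wrong error rates for the daily results as such. The documents do not support that. A t-test or ANOVA on one day uses one value per patient and holds 5%. MANCOVA can take the days as a correlated outcome vector, and with complete data the corresponding multivariate test also holds 5%. It would be wrong to say that none of the named methods can allow for within-patient correlation.

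Nor does any section say that patient-days will be pooled. The nearest text points the other way: 9.1.1 defines one total per patient, and 9.3.1 sizes the trial by "assuming a 2-sided test of two independent sample means with α 0.05". The pooled figures therefore describe an analysis that the wording leaves open, not one that is planned. Likewise, 9.3.2 does not state that any significant day would count as success.

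The six-day figures also assume the longest schedule for everyone. The documents guarantee less, so the three-day range belongs beside them. A mixed model alone would not cure the any-day inflation; the single pre-named contrast does.

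All of this stands, and it narrows the point. What it does not answer is that outcomes listed as primary have no day, summary, multiplicity rule or treatment of post-discharge days.

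**Conclusion.** The point holds as a gap in specification with measurable consequences. For each outcome, unadjusted day-by-day testing gives at least one false-positive day in about 11 to 14% of trials with 3 days and 17 to 25% with 6 days. Pooling, if it were done, would give about 12 to 20% or 22 to 37%. These ranges rest on an assumed ρ of 0.3 to 0.7, equal correlation between days, normal data, complete days and a 20 v 40 split. They do not apply to a single daily test taken alone, to the total in 9.1.1, or to the power statement in 9.3.1. MANCOVA is valid for complete vectors, but it gives no single effect estimate and ordinarily loses patients discharged early. The wording should be settled before the data are analysed. The gap does not invalidate the trial's main opioid comparison.

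**What to change.** In 9.3.2:

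1. Keep the one-value-per-patient total as the primary opioid test, and state its time window, since 9.1.1 uses the hospital stay and 9.3.1 uses 72 hours.
2. For daily opioid use and each pain scale, fit one linear mixed model with group, day and group × day, a within-patient covariance, and all observed days. Patients discharged early then stay in the analysis. The model assumes that discharge is explained by the values already observed, and this should be stated.
3. Name one contrast per outcome: the group difference averaged over the first 72 hours after surgery. Define it from the same starting time as the 9.3.1 total, and include the day of surgery where data exist; calendar days 1 to 3 could leave out those hours. An expected stay of more than 3 days limits missing data in this window. For opioid use with complete data, the contrast is the 72-hour total divided by the number of days, so it should be labelled as supporting that comparison, not as a separate success criterion.
4. Report day-by-day estimates with confidence intervals as descriptive only.

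This controls error within each outcome. Whether to adjust across the opioid and pain outcomes is a separate decision, which the plan should also record.

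Cost: SAP wording, a little more analysis work with standard software, and no day-specific significance claims. No new data are needed.
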